Setting: The POSH Clinic is an interdisciplinary collaboration between surgery, anesthesiology, geriatrics, nursing, and physical therapy to provide perioperative surgical care for high-risk Veterans at the Durham VAMC. The clinic opens with a conference to review patients to be seen that day. The surgery chief resident presents and the team covers technical issues with the surgery and selection of anesthesia, as well as covering a list of specific care points. The POSH clinic estimates 200 – 400 patients enrolled annually.

VAPOSH Veterans who are malnourished or at risk of being malnourished will be randomly assigned on a 1:1 ratio by computer-generated random numbers to either an education (nutritional counseling) control (PoshControl) arm or high-protein perihabilitation (PeriHab) arm. All will receive nutrition education. Participants in the PeriHab arm will also be provided with high quality protein supplements that will bring their protein intakes to at least 30 grams for each of the 3 meals per day.

Study Arms:

- PoshControl; n = 42: During their VAPOSH clinic visit, participants will be provided nutrition counseling and prescribed to consume protein at 1.0 g/kg of body weight in the form of educational handouts explained by a Registered Dietitian. Participants will also be instructed to consume 1 oral nutrition supplement per day two weeks before surgery.
- PeriHab; n = 42: PeriHab will be provided nutrition counseling and prescribed to consume protein at 1.6 g/kg of body weight) as well as provided 30 g of high quality protein to some 3 times per day for 2 weeks before and 4 weeks after surgery.

Measurements:

After the participant has been consented and HIPAA Authorization forms have been signed, a Registered Dietitian will administer the NRS-2002 screening tool, the PG-SGA, and nutrition focused physical exam. A patient screening “nourished” on the NRS-2002, PG-SGA, and nutrition focused physical exam will not be included in the study. For study candidates who are malnourished or at nutritional risk we will then proceed with baseline assessments (described below). Upon the completion of all baseline assessments, the participant will be randomized to PeriHab or PoshControl. The following variables will be blocked in this order: 1) surgery type and 2) American Society of Anesthesiology (ASA) Physical Status Classification System (≥ 3 versus < 3). An equal number of participants will be randomized across the two arms.

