 - Feasibility Hypothesis: $\geq 75\%$ of patients approached for recruitment will agree to participate

Fidelity proportions will be calculated for adherence and retention at the end of the intervention using the following:

1. Proportion adherent to nutrition intervention will be computed by the number of empty supplement containers divided by the number of possible supplement containers that could be consumed.

2. Proportion adherent to nutrition intervention will also be computed by the number of meals consumed that are 25 grams of protein divided by the number of possible meals that could be achieved. For the PoshControl arm, adherence will be assessed by the number of dietary changes they make based on the educational handout provided to them at baseline. These will be determined by using diet records for 3 days prior to surgery and 3 days following surgery. Diet food records are valid method for collecting dietary intake data and have been administered in Veteran populations.⁴² We have experience administering and analyzing this data.¹

- Adherence Hypothesis: $\geq 75\%$ of the time PeriHab participants will adhere to the intervention and $\geq 75\%$ of the time controls will show at least one recommended dietary change in their 3-day diet record

3. Proportion retention will be computed by dividing the number of retained subjects at the end of the intervention by the total number randomized into the study.

- Retention Hypothesis: $\geq 80\%$ of participants will remain in the study for the duration of the trial

We will calculate these rates of retention and adherence and their respective confidence intervals overall and by group. While non-powerful, we will assess if these rates differ by chi-square test of proportion and Poisson regression respectively. In a series of sensitivity tests, we will assess if adherence overall was impacted by demographic or symptomatic variables (such as chronic health conditions, living arrangements, surgery, functional status, and nutrition status).

Acceptability will be assessed by:

1. Calculating levels of attrition.

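### The meal adherence measure uses 25 g against a 30 g target, and adherence defined differently by arm is pooled and compared with no common measure designated

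*Combined protocol and SAP*

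**What the plan says.** The fidelity part of the Aim 2.1 Analysis Plan gives two ways to compute adherence. Item 1, the container measure, is the "number of empty supplement containers divided by the number of possible supplement containers that could be consumed"; it names no arm. Item 2, the meal measure, is the "number of meals consumed that are 25 grams of protein divided by the number of possible meals that could be achieved". For PoshControl, item 2 says that "adherence will be assessed by the number of dietary changes they make based on the educational handout", and the adherence hypothesis turns this into the expectation that, at least 75% of the time, "controls will show at least one recommended dietary change in their 3-day diet record". For PeriHab the hypothesis is adherence at least 75% of the time, with neither measure named.

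The same section then calculates retention and adherence rates with "their respective confidence intervals overall and by group". It calls the arm comparisons non-powerful but plans them: "we will assess if these rates differ by chi-square test of proportion and Poisson regression respectively", which assigns Poisson regression to adherence. It adds sensitivity tests in which "we will assess if adherence overall was impacted by demographic or symptomatic variables".

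The PeriHab target is set out under Setting: supplements are to "bring their protein intakes to at least 30 grams for each of the 3 meals per day". The PeriHab arm protocol provides three 30 g supplements a day, and weekly contacts counsel participants who have difficulty so that they reach 30 g three times daily.

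**The concern.** There are two gaps. First, a meal with 25 g to under 30 g of protein misses the stated target but counts as adherent if the 25 g cut is read as a minimum. No tolerance or reason is given. With two PeriHab measures and one 75% criterion, the choice of deciding measure stays open until the data are seen, and the lower cut makes the meal measure more lenient than the target.

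Second, PeriHab is scored as a fraction of containers or meals, while control is scored on dietary changes: a count with no stated denominator in item 2, and a yes/no per record in the hypothesis. A Poisson rate ratio needs the same event and exposure unit in both arms. If the arm-specific definitions enter the overall rate, the arm comparison or the patient-factor models, the results reflect the definitions as well as behaviour. Fidelity is a stated objective of Aim 1.1 and is meant to inform a larger trial.

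**Working it through.** The plan states no power or precision figure for adherence, so there is none to reproduce. Its only power figure, a detectable standardized difference of 0.634 with 40 per group, concerns physical function. It reproduces (0.6343 by the noncentral t) and does not depend on what follows.

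**Meal cut.** Let R25 and R30 be the shares of meals reaching 25 g and 30 g, and b the share from 25 g to under 30 g. Then R25 = R30 + b with b ≥ 0, so R25 can never be below R30. R30 is under 75% only if b > R25 − 75:

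- R25 = 80%: b must exceed 5 points
- R25 = 85%: b must exceed 10 points
- R25 = 90%: b must exceed 15 points

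Assuming scoring from two three-day records, each participant has 3 × 3 × 2 = 18 meals, and those shares are 0.05 × 18 = 0.9, 0.10 × 18 = 1.8 and 0.15 × 18 = 2.7 meals. The documents give no distribution of protein per meal, so b is unknown.

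**Bound from the supplements.** Assume each supplement is taken with a meal, and let c be the share of meals taken with a full 30 g container. Those meals pass both cuts, so R30 ≥ c and b ≤ 1 − c:

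- c = 90%: b is 0 to 10 points
- c = 75%: b is 0 to 25 points
- c = 60%: b is 0 to 40 points

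On this assumption R30 is below 75% only when c is also below 75%. The case that matters is therefore container use under 75% while the 25 g meal rate reads 75% or more: the two measures then disagree, and the plan does not say which one decides.

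**Definitions by arm.**

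- PeriHab: containers used over containers possible, or qualifying meals over possible meals.
- PoshControl: number of handout-based changes, or one or more such changes in a record.
- Overall rate, Poisson comparison, patient-factor models: adherence, measure not specified.

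If both arms were scored from two records (assumption), the units would be 42 × 18 = 756 meals in PeriHab and 42 × 2 = 84 yes/no records in control. These are different events, so neither their pooled proportion nor their ratio has a clear meaning.

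**Could the container ratio serve both arms?** It can be formed in both:

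- PeriHab: 3 × 14 = 42 before surgery and at most 3 × 28 = 84 after, 126 in total. The post-surgery supply is handed over at discharge, so a stay of L days leaves at most 126 − 3L, for example 111 at L = 5 and 96 at L = 10.
- Control: 1 × 14 = 14, all before surgery.

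The PeriHab ratio thus covers up to six weeks including recovery, and the control ratio two weeks before surgery. Restricting both arms to the pre-surgery period removes that difference, leaving 42 versus 14 containers. A crude pooled rate would then give PeriHab 42/(42 + 14) = 75% of the weight when arms are equal in size; averaging each participant's own proportion avoids this.

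**The case against.** The best defence is that the plan already contains a usable common measure. Item 1 is not confined to PeriHab, and controls are prescribed one supplement a day and return lids on the day of surgery. This stands, so it would be wrong to say that no common measure exists. What is missing is its designation for the overall, between-arm and patient-factor analyses, and the control hypothesis rests on dietary changes alone.

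The 25 g cut may also be a deliberate allowance: the introduction to Aim 1.2 speaks of about 30 g, and food records are self-reported. That is plausible, but no tolerance is written down. It is also fair that the container measure would expose much of any shortfall, so a reader should not infer that the lower cut hides poor adherence.

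Two other stronger readings are tempting. One is that 126 or 42 containers against 14 distorts the arm comparison. It need not: item 1 divides by possible containers, and a Poisson model with an offset handles unequal exposure; only a crude pooled rate is reweighted. The other is that three 25 g meals put PeriHab at the control prescription. At an assumed 75 kg that is 75/75 = 1.00 g/kg, but three 30 g meals give 90/75 = 1.20 g/kg, also short of 1.6, and protein outside meals is ignored. The calculation does not show harm from the lower cut.

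Finally, the plan reports rates by group and admits low power. The by-group rates remain useful, but low power does not settle what an overall rate or arm contrast measures.

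**Conclusion.** The point holds in this form. The meal measure is scored below the protocol's own target without a stated reason, the 75% criterion is not tied to one of the two PeriHab measures, and no common measure is designated for the overall rate, the between-arm test or the models of overall adherence.

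The size of the first part is unknown. The excess of the 25 g rate over the 30 g rate equals the share of meals between the cuts. If supplements are taken with meals, that share is at most the share of meals without a full container. The second part is a gap in definition and does not depend on any assumed rate.

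The impact is confined to the pilot's fidelity results. A reader might infer that the efficacy conclusions or the sample size are compromised; the documents do not support that, because the Aim 1.2 intent-to-treat analysis and the power calculation do not use these adherence rates.

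**What to change.** 1. Score PeriHab meals at 30 g or more, keep 25 g or more as a labelled sensitivity cut, and state whether the container or the meal measure is compared with the 75% criterion.
2. Report each arm's own adherence definition by arm only, with its confidence interval and against its own criterion. Do not pool these definitions or test them against each other.
3. For the overall rate and the between-arm test, use the proportion of prescribed pre-surgery containers used, calculated per participant. Analyse PeriHab post-surgery adherence, and the patient factors related to it, within that arm, so that those weeks are not discarded.

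The cost is SAP wording. Both arms already return lids on the day of surgery, and three-day food records are scheduled at all three visits. The reported meal adherence may be lower, the Poisson comparison of the arm-specific definitions is given up, and the common measure says nothing about the weeks after surgery.

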Measures and Data Collection Points

| Measure | When Collected |
|------------------------------------|-----------------------|
| NSR-2002 | Baseline (T1), T2, T3 |
| PG-SGA | T1, T2, T3 |
| Nutrition Focused Physical Exam | T1, T2, T3 |
| Cognition | T1 |
| Medical History | T1 |
| Demographic | T1 |
| Anthropometrics | T1, T2, T3 |
| Comorbidity Status | T1 |
| Bristol Stool Chart | T1 |
| Short Physical Performance Battery | T1, T2, T3 |
| Handgrip strength | T1, T2, T3 |
| Biological Markers | T1, T2, T3 |
| Postoperative outcomes | T3 |

| | |
|---|----------------------------|
| Physical Activity | T1, T2, T3 |
| PROMIS and PROMIS GLOBAL QUESTIONNAIRES | T1, T2, T3 |
| Three-day Food Record | T1, T2, T3 |
| Protein Checklist | Daily |
| 24-Hour Dietary Recall | Weekly between time points |
| Participant Satisfaction Questionnaire | T3 |
| Participant Acceptability | T3 |

Risk/Benefit Assessment

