Any Veteran who contacts or is contacted by study staff will be told that their participation is voluntary, and they may choose not to answer any questions that they find too sensitive. Also, Veterans will be told that their participation will not affect their care at the VA. The study staff member will explain the study in detail, including compensation. No study procedures will begin until formal, written informed consent has been obtained.

Consent Process

On the day of their POSH clinic visit, potential participants identified we will be informed again that he or she is being recruited because he/she is having abdominal elective surgery and is a patient in the POSH clinic. The participant will be told that their participation is voluntary, and they may choose not to answer any questions that they find too sensitive. Also, Veterans will be told that their participation will not affect their care at the VA. The study staff member will explain the study in detail. The participant will be given as long as they need to read through the consent form and HIPAA Authorization. Study staff will answer all questions and concerns. No study procedures will begin until formal, written informed consent has been obtained.

Study Interventions

Caloric Intake and Monitoring Protocol for Both Arms: Caloric needs will be prescribed for each participant using an established standard of 30 to 35 kcal/kg⁴¹ at the VAPOSH clinic. To assure adequacy for all enrollees, calculated protein needs will be higher than the recommended 0.8 g/kg of body weight for both arms, **PoshControl** protein prescription = **1.0 g/kg of bodyweight** and **PeriHab** protein prescription = **1.6 g/kg of bodyweight**. Participants will be monitored by weekly phone calls during which study staff will ask the participant to recall their intake from the day before (24-hour dietary recall). This information will be used to ensure that both arms are meeting their calorie needs. If a participant in either arm has an inadequate intake they will be counseled on how to increase their current intake. Based on our previous assessment of similar populations, it is unlikely that the **PeriHab** arm will be able to meet the 1.6 g/kg of body weight protein prescription on their own and for that reason we are providing protein supplement to be consumed 3 times a day (as described below). The **PoshControl** arm will be given one ONS to consume every day prior to surgery.

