PeriHab Arm Protein Perihabilitation Protocol: The protein supplementation protocol provides for three daily supplements of 30 g of high quality protein in the form of a liquid nutritional supplement (30 g). Subjects will receive sample menus to help the participants incorporate the increased protein into their daily intake. Individually packaged portions of the liquid supplement will be supplied at the VAPOSH clinic visit (T1). Participants will be given a two-week supply of supplement. Included will be a printed check-off sheet for participants to record protein supplement use. The protein check-off sheet, three-day food record, Actigraph log, and lids from the protein drink will be turned in on the day of surgery (T2). Following their surgery, participants will be given an additional four week supply of the same supplement at discharge and the same materials as at the VAPOSH clinic visit (T1). The protein check-off sheet, three-day food record, Actigraph log, and lids from the protein bottles will be turned in at the follow-up appointment (T3).

Participants will be contacted weekly by study staff and queried with a standard set of open-ended questions designed to identify problems with compliance. Participants who are having difficulty will be provided additional counseling to ensure they are able to achieve 30 grams of high quality protein three times a day.

PoshControl Arm Protocol: Participants in the PeriControl arm will be asked to consume 1 ONS protein supplement per day prior to surgery. They will be provided education on the role of nutrition to prepare for and heal from surgery with the following main messages, 1) complications associated with malnutrition; 2) the benefits of good nutrition; 3) tips for dietary intake when not hungry; 4) easy food preparation; and 5) what to eat. The study Registered Dietitian will instruct the participant to follow the information on the handout. Study staff will call the PoshControl arm participants once a week to identify problems with compliance,

answer any questions and also remind participant to complete their 3-day food records. The ONS check-off sheet, three-day food record, and lids from the Ensure Plus bottles will be turned in on the day of surgery (T2). Four weeks following surgery, PoshControl participants will return for a follow-up appointment and will bring Ensure Plus checklist, three-day food record, and Actigraph log.

Adverse Events

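### The control arm's 75% adherence target counts any one dietary change and leaves out the daily supplement, so meeting it is weak evidence of fidelity to the control condition

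*Combined protocol and SAP*

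**What the plan says.** **Target.** The Aim 2.1 Analysis Plan (fidelity, adherence hypothesis) expects that at least 75% of the time "controls will show at least one recommended dietary change in their 3-day diet record".

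**Measurement.** The same section says that for PoshControl "adherence will be assessed by the number of dietary changes they make based on the educational handout provided to them at baseline", determined by "using diet records for 3 days prior to surgery and 3 days following surgery". It does not say which changes qualify, how large they must be, which record is the reference, or whether the 75% counts participants, records or days.

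**Control condition.** Study Arms and Study Interventions give controls a protein prescription of 1.0 g/kg, a caloric prescription of 30 to 35 kcal/kg, nutrition education and a supplement: the PoshControl "arm will be given one ONS to consume every day prior to surgery". The education has five main messages, beginning "1) complications associated with malnutrition; 2) the benefits of good nutrition; 3) tips for dietary intake when not hungry" and ending with food preparation and what to eat.

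**Data collected.** The measures table lists "Three-day Food Record | T1, T2, T3", so a baseline record exists. Under PoshControl Arm Protocol, "The ONS check-off sheet, three-day food record, and lids from the Ensure Plus bottles will be turned in" on the day of surgery (T2). The first fidelity item in the Aim 2.1 plan is a container proportion, empties over the number that could have been used. It is not restricted to PeriHab, but no control target is attached to it.

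**The concern.** Fidelity is one of the three things that Aim 1.1 sets out to evaluate, and the control arm's fidelity figure should show whether controls received and followed what they were assigned. The stated criterion is loosely connected to that. One change of any size is enough, and with no named reference record it is unclear what the change is from. Two of the five education messages (complications of malnutrition, benefits of good nutrition) name no eating behaviour that a food record could show. None of the three quantifiable instructions (ONS, protein per kg, calories per kg) enters the target. A control who takes few of the supplements and misses the protein prescription could still count as adherent.

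The figure is also used elsewhere. Adherence rates are to be reported with confidence intervals overall and by group and compared between groups. Adherence variables enter the planned mediation analyses, and level of compliance defines the per-protocol analysis. A favourable control figure that does not reflect uptake of the control condition could mislead in any of these, and in the design of the larger trial.

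**Working it through.** **1. The plan's own figure.** The 75% is stated without a derivation or a background rate, so there is nothing to reproduce. Both arms receive nutrition education, so the trial has no uneducated group from which to estimate a background rate. The one derived figure in the plan, a detectable difference of 0.634 SD with 40 per group, does reproduce (0.6343 by a two-sample t-test) but does not bear on this point.

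**2. Target set against control condition.**

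| Instruction to controls | In the 75% target? | Data already planned |
|---|---|---|
| One ONS a day before surgery | No | Lids and check-off sheet at T2 |
| Protein 1.0 g/kg | No | Food records at T1, T2, T3; weekly 24-hour recalls |
| 30 to 35 kcal/kg | No | Same |
| Education handout | Yes, any one change | Food records; T1 not named as reference |

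**3. How easily could chance meet the target?** The documents give neither the number of scorable items, k, nor the probability, p, that an item shows a spurious change in a record. Both are assumptions here, and items are treated as independent. I use k = 3 (the education messages that concern eating) and k = 5 (a longer list). With one record, P(at least one) = 1 − (1 − p)^k. If a change in either of two records counts, the exponent is 2k.

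- k = 3, p = 0.20, one record: 1 − 0.8³ = 1 − 0.512 = 49%.
- k = 5, p = 0.20, one record: 1 − 0.8⁵ = 1 − 0.328 = 67%.

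Share of controls passing with no true adherence:

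| p | k = 3, one record | k = 5, one record | k = 3, either record | k = 5, either record |
|---|---|---|---|---|
| 0.10 | 27% | 41% | 47% | 65% |
| 0.20 | 49% | 67% | 74% | 89% |
| 0.30 | 66% | 83% | 88% | 97% |
| p giving 75% (1 − 0.25^(1/exponent)) | 0.37 | 0.24 | 0.21 | 0.13 |

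**4. Chance that the arm meets the target.** Take the participant as the unit and all 42 controls as scored. Then 0.75 × 42 = 31.5, so 32 must pass. The binomial probability of 32 or more, using the shares above, is:

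| p | k = 3, one record | k = 5, one record | k = 3, either record | k = 5, either record |
|---|---|---|---|---|
| 0.10 | <0.1% | <0.1% | <0.1% | 9% |
| 0.20 | <0.1% | 14% | 44% | 99.6% |
| 0.30 | 10% | 92% | 99% | >99.9% |

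The answer runs from almost never to almost always over plausible inputs, and the plan gives nothing that would locate the trial in this range.

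**5. Which record is scored.** The Aim 2.1 plan specifies "using diet records for 3 days prior to surgery and 3 days following surgery". The schedule lists "Three-day Food Record | T1, T2, T3", and the control protocol says "Four weeks following surgery, PoshControl participants will return for a follow-up appointment", bringing the food record. A record covering the three days after the operation and one returned at four weeks are different records, and the documents do not say which is meant.

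**The case against.** The strongest reply is that the plan is not short of control-arm fidelity data. The container proportion is not limited to PeriHab and will be reported by group. Controls return lids and check-off sheets, have weekly 24-hour recalls, and keep food records at all three time points. Dietary intake is itself a secondary outcome. That is right. A reader might infer that the pilot could not tell whether controls took up the control condition, but the documents do not support this: the weakness lies in the target, not in the data.

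Other strong readings also fail:

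- **The target is passed almost automatically.** This is not shown. With three items, one record and p = 0.20, 49% of controls pass, well short of 75%. The two-record rule is only one reading, since the hypothesis refers to a single 3-day record.
- **ONS is the only countable instruction.** It is not. Protein per kg and calories per kg are also prescribed.
- **A control who takes no ONS is still scored adherent.** The withdrawal section removes subjects who refuse the protein supplement, and that rule is not arm-specific. It may catch outright refusal, but not low intake without refusal.
- **The operation itself produces the change.** Surgery cannot explain a change in the pre-surgery record. The documents do not say that post-surgery changes go in the recommended direction, and the post-surgery record may be the one at four weeks.

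It is also fair to say that this arm is an education control, so removing dietary change from its adherence target would leave the education untested. The fix keeps it for that reason.

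The core of the concern still stands: no target for controls is tied to the container proportion, to a T1 comparison or to the protein prescription.

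**Conclusion.** The concern holds as a criticism of this one target. Followed as written, it could give a favourable control adherence figure that does not reflect uptake of the control condition, because any one unlisted change passes, no reference record is named, and the daily ONS is left out. These defects can be read directly from the text and need no assumption.

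Their numerical effect cannot be derived from the documents. The illustrative 49% (3 items) and 67% (5 items) rest on an assumed p of 0.20, independence between items and one scored record. They show that chance can contribute materially, not that it will meet the target. The point does not affect the sample size or the Aim 1.2 primary analysis. It should be corrected before the fidelity results are produced.

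**What to change.** 1. State that the container proportion (first fidelity item, Aim 2.1 Analysis Plan) applies to PoshControl: ONS consumed divided by ONS expected from T1 to surgery, from the lids and check-off sheet returned at T2. Attach the 75% control target to it. Recruitment allows surgery more than two weeks after the clinic visit, so say how the expected number is counted in that case.
2. Keep dietary change as a second control measure, scored against the T1 food record on a pre-listed set of food-level handout recommendations. State the unit to which the percentage refers.
3. Report control protein intake against the 1.0 g/kg prescription from the food records already collected.
4. Reconcile the post-surgery window in the Aim 2.1 plan with the T3 record at four weeks.

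**Cost.** Wording in the analysis plan and a short scoring list; no new data and no change in sample size. There are two downsides. The control adherence figure may be less favourable. The ONS measure covers only the period before surgery, so items 2 and 3 have to carry the post-surgery period.

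### Adherence is to be compared between arms by Poisson regression with no participant-level variance, so its standard errors may be too large or too small, depending on a within-person correlation the plan does not give

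*Combined protocol and SAP*

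**What the plan says.** All of this stands in the combined protocol and SAP, under Aim 2.1 Analysis Plan, in the part on fidelity.

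- **Adherence, first measure:** "the number of empty supplement containers divided by the number of possible supplement containers that could be consumed".
- **Adherence, second measure:** "number of meals consumed that are 25 grams of protein divided by the number of possible meals that could be achieved".
- **PoshControl arm:** "adherence will be assessed by the number of dietary changes they make based on the educational handout provided to them at baseline", taken from "diet records for 3 days prior to surgery and 3 days following surgery".
- **Estimates:** "We will calculate these rates of retention and adherence and their respective confidence intervals overall and by group". No interval method is named.
- **Tests:** "we will assess if these rates differ by chi-square test of proportion and Poisson regression respectively". Since retention is listed first and adherence second, retention gets the chi-square test and adherence the Poisson regression. No offset, dispersion term, robust variance or participant effect is mentioned.
- **Predictors:** as sensitivity work, "we will assess if adherence overall was impacted by demographic or symptomatic variables". No model is named for this.

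The success criterion is adherence of at least 75%. The mixed models described later belong to the Aim 1.2 outcomes and do not cover adherence.

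**The concern.** A Poisson model sets the variance of a count equal to its mean. Container and meal adherence depart from that in two opposing ways. Each count has a ceiling, which makes the true variance smaller than Poisson. One person's containers or meals also tend to be taken or missed together, which makes it larger. The two departures cancel only by coincidence, so a plain Poisson standard error can be too wide or too narrow.

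At stake are the p-value for the arm comparison and, if the same variance is carried over, the by-group confidence intervals read against 75% and the search for predictors of poor adherence. All three are meant to inform a larger trial.

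**Working it through.** **The plan's own figure.** None is given for adherence. The only design figure, a detectable difference of 0.634 SD with 40 per group, concerns physical function. A two-sample t calculation reproduces it (0.634), but it has no bearing here.

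**Inputs**

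- Participants: n = 42 per arm (Study Arms).
- Adherence: p = 0.75, the hypothesised minimum.
- Containers possible, from Study Arms: PeriHab 3 × 7 × (2 + 4) = 126, ignoring days in hospital; PoshControl 1 × 14 = 14.
- Meals possible: 3 + 3 diet-record days at 3 meals a day = 18 per person.
- Between-person SD of true adherence: **assumed**, 0 to 0.30. It converts to a within-person correlation by ρ = SD² / [p(1−p)]. SD 0.15 gives 0.0225/0.1875 = 0.12, and SD 0.30 gives 0.09/0.1875 = 0.48.

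**Formulas.** For m possible units per person, the Poisson variance is mp and the true variance is mp(1−p)[1+(m−1)ρ]. Their ratio, true over Poisson, is

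D(m) = (1−p)[1+(m−1)ρ].

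For a log rate ratio between two groups of equal size, the Poisson SE divided by the true SE is

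R = √{(1/m₁ + 1/m₂) / (D(m₁)/m₁ + D(m₂)/m₂)},

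and the type I error is approximately 2[1 − Φ(1.96R)].

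**No between-person variation (ρ = 0).** D = 0.25 for every m, so R = 2 and the type I error is about 0.01%.

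**Between arms, 126 vs 14 containers.** 1/126 + 1/14 = 0.0794 + 0.7143/10 needs no rounding if everything is multiplied by 126: the Poisson term is 1 + 9 = 10.

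- SD 0.15: D(126) = 0.25 × 16 = 4.00 and D(14) = 0.25 × 2.56 = 0.64. True term 4.00 + 9 × 0.64 = 9.76. R = √(10/9.76) = 1.01; type I error 4.7%.
- SD 0.30: D(126) = 0.25 × 61 = 15.25 and D(14) = 0.25 × 7.24 = 1.81. True term 15.25 + 9 × 1.81 = 31.54. R = √(10/31.54) = 0.56; type I error 27%.
- Break-even: 0.25(1+125ρ) + 9 × 0.25(1+13ρ) = 10 gives 242ρ = 30, so ρ = 0.124, or SD 0.15.

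**Between arms, 18 vs 18 meals.** Here R = 1/√D.

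- SD 0.15: D = 0.25 × 3.04 = 0.76, R = 1.15, type I error 2%.
- SD 0.30: D = 0.25 × 9.16 = 2.29, R = 0.66, type I error 20%.
- With 9 meals instead, SD 0.30 gives D = 0.25 × 4.84 = 1.21, R = 0.91, type I error 7%.

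**Conditional case: predictors within PeriHab, 21 vs 21, 126 containers each.** This applies only if Poisson is also used for the predictor work. SD 0.15 gives R = 1/√4.00 = 0.50 and 33%. SD 0.30 gives R = 1/√15.25 = 0.26 and 62%.

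| Comparison | SD 0 | SD 0.15 | SD 0.30 |
|---|---|---|---|
| Arms, 126 vs 14 containers | ~0% | 5% | 27% |
| Arms, 18 vs 18 meals | ~0% | 2% | 20% |
| Within PeriHab, if Poisson is used | ~0% | 33% | 62% |

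**Simulation check.** Beta-binomial data, 42 per arm, 126 vs 14 containers, 40,000 replicates: the plain Poisson test gave 0.01% at ρ = 0, 3.1% at 0.1, 10.3% at 0.2 and 28.1% at 0.5, in line with the formula. The same regression with participant-level robust variance gave 4.3% to 5.3% over ρ from 0 to 0.5. A single common dispersion factor did not repair the test when denominators differed: type I error fell to about 0.3% at ρ of 0.1 and above.

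**Interval for PeriHab container adherence.** With Poisson variance pooled over containers, the 95% half-width is 1.96√[0.75/(42×126)] = 2.3 points. Across participants it is 1.96√{0.1875[1+125ρ]/(126×42)} = 4.7 points at SD 0.15 and 9.1 points at SD 0.30.

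**Sensitivity to the schedule.** Specific Aim 1.2 describes supplementation for two weeks after surgery, whereas Study Arms says four. These statements must be reconciled, since they set the denominator. With 3 × 28 = 84 containers, the between-arm figures at SD 0.15 and 0.30 become 4% and 26%, so the conclusion does not depend on which is meant.

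**The case against.** **Poisson regression is not wrong in itself.** With a log(possible units) offset and participant-level robust variance it is valid, as the simulation shows. The plan is silent on both, so the gap is one of specification. This stands, and the fix allows that route.

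**A reader might infer that the test will produce false positives.** The documents do not support that for the test actually named. At SD 0.15 the between-arm container test is about nominal and the meal test conservative; inflation needs larger variation, and no SD is given. SD 0.30 around a mean of 0.75 is a wide spread, and withdrawing participants who refuse the supplement could trim its lower tail. Only an error in either direction is shown.

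**A reader might take 33% to 62% as the size of the problem.** Those figures concern a predictor analysis for which the plan names no model, and the 21 vs 21 split within PeriHab is a construct for illustration. They hold only if Poisson is used there too.

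**A reader might infer that the intervals will be pooled over containers.** The plan states no interval method, so that is a risk to close and not an error found.

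**The bounded-count argument does not reach every measure.** The number of dietary changes in PoshControl has no stated ceiling, and Poisson is a natural choice for it. It also shares no scale with PeriHab container or meal adherence, and no choice of model repairs a comparison across different measures. The 126 vs 14 case assumes that control containers enter the test, which the text permits but does not settle.

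**The stakes are limited.** The 75% criterion is a rate and does not use the Poisson p-value; the plan concedes low power for the comparison and calls the predictor work sensitivity testing. This lowers the severity. It does not answer the point, because low power warns of missed effects and not of a miscalibrated error rate.

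**Conclusion.** The concern holds for container and meal adherence analysed with ordinary Poisson standard errors, the plain reading of the text. At 75% adherence those standard errors are twice too large with no between-person variation and too small when variation is large. Over an assumed between-person SD of 0 to 0.30, the between-arm type I error runs from about 0% to 27% for 126 vs 14 containers and from about 0% to 20% for 18 meals. It is close to 5% near SD 0.15 for containers and, from D = 1 at ρ = 3/17 = 0.18, near SD 0.18 for meals.

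The direction of the error cannot be settled from the documents. The result rests on the assumed SD, p = 0.75, full schedules as denominators, and a common measure in both arms. Severity is modest: the analysis should be specified better, but the trial's main conclusions do not depend on it.

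**What to change.** Replace the Poisson sentence with a participant-level specification:

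- For containers and for meals, compute one adherence proportion per participant and compare arms by Welch's test. Alternatively, fit a fractional or quasi-binomial model, or Poisson with a log(possible units) offset, in each case with participant-level robust standard errors. A single common dispersion factor is not enough when the arms have different denominators.
- Use the same basis for the overall and by-group confidence intervals set against 75%, and for the predictor analyses, naming the model for the latter.
- Compare arms only on a measure defined the same way in both. Report the number of dietary changes separately, within PoshControl.
- State the possible number of containers and meals per participant.

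The cost is analysis wording only; no new data are needed. The drawback is that intervals will usually be wider.
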